8.4. Visit Windows

For visit windows see Table 1: Schedule of Assessments in Section 4.6 of this SAP.

8.5. Pooling of Centers

Summaries will be provided pooled for all centers by treatment group if not indicated otherwise.

8.6. Subgroups

Descriptive summaries of efficacy for the primary efficacy endpoint and for the key secondary efficacy endpoints will be repeated on the subgroups of COVID-19 severity (moderate and severe), age-class (<65 years and <65 years), vaccination status (vaccinated and not vaccinated), patients taking Dexamethasone and/or Remdesivir during treatment with study drug, and obesity risk factor (BMI <30.0 kg/m² and BMI >=30.0 kg/m²). Additionally, baseline characteristics will be summarized for these subgroups.

This document is confidential.

9. Demographic, Other Baseline Characteristics and Medication

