Please note: Patients who are receiving oxygen therapy at baseline for a chronic condition (eg, emphysema, chronic obstructive pulmonary disease (COPD), pulmonary arterial hypertension [PAH], idiopathic pulmonary fibrosis [IPF], etc.) should be considered as having severe COVID-19 (unless the

This document is confidential.

SAP Text Version: 2.0, 31-Aug-2022 Controlled Document ID: CCI , Effective Date 31-Aug-2020 Filing requirements: TMF

Page 13 of 56

patient meets the definition for critical COVID-19). For questions related to COVID-19 severity, the investigator should contact the medical monitor.

Each site will treat all patients with SoC for the duration of the study. The selected SoC will be used in accordance with the hospital's SoC procedures and may include drugs under an emergency use authorization.

This study consists of 3 periods: (1) screening, (2) treatment, and (3) follow-up. During the screening period, each potential patient (or patient's legally acceptable representative) will provide informed consent prior to starting any study-specific procedures. The randomization of patients to treatment groups will be performed centrally by an interactive web-response system (IWRS) using a randomization scheme that will be developed by an unblinded, independent statistician. During the treatment period, randomized patients will be provided their assigned treatment and assessments according to the protocol. All patients will be treated for 28 days, unless the study drug is discontinued, eg, for safety reasons. If the patient is discharged home before Day 28, the study team will provide the patient with the remainder of the blinded study drug kits to take home along with instructions on how to continue treatment at home on the day-of-discharge; for these patients, treatment compliance will be conducted via a diary. If the patient does not feel comfortable to complete the diary, the site will alternatively provide the patient with the option to be called, twice a day, to confirm that the study drug is taken as instructed. The treatment period will end with the Day 28 (End of Treatment Visit) assessments. The follow-up period will end with the Follow-up Visit assessments on Day 60.

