5.1. Primary Efficacy Endpoint

The primary efficacy endpoint of this study is:

Proportion of patients with disease progression on Day 14. Disease progression is defined as the
proportion of patients who are not alive or who have respiratory failure. Respiratory failure is defined
as patients who have a score of 2, 3 or 4 on the National Institute of Allergy and Infectious Diseases
(NIAID) 8-point ordinal scale (see below).

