7.1. Primary Efficacy Endpoint

The main estimand for the primary efficacy endpoint is defined as follows:

- Treatment: 300 mg MP1032 BID plus SoC in Arm A and placebo BID plus SoC in Arm B. If a patient terminates the study treatment, but still remains in the study and is followed up, then the patient will continue to receive either SoC alone or SoC+additional treatment. These treatments are defined with regards to intercurrent events as 'other treatments'.
- Population: Of all patients defined by the study inclusion / exclusion criteria, the analysis population will include all randomized patients (ITT population).
- Variable: A binary variable indicating disease progression (respiratory failure) when having completed Day 14 assessment or died prior to Day 14. Respiratory failure is defined as patients who have a score of 2, 3 or 4 on the NIAID 8-point ordinal scale.
- Intercurrent events: All events leading to study treatment discontinuation and/or switch to other treatment prior to Day 14 will be handled using the treatment-policy strategy (ie, the observed NIAID score at Day 14 will be used for definition of the failure in such patients).
- Population-level summary: Common risk difference resulting from the Mantel-Haenszel (MH) test
 considering the 4 strata out of the combinations of the 2 randomization stratification factors disease
 severity (moderate versus severe) and age-class (<65 years versus >65 years) at baseline.

Missing data on Day 14 resulting from study termination prior to Day 14 are not expected. However, in case it happens, such monotone missings will be imputed by multiple imputation using information from similar patients of the same treatment group assuming 'missing at random' (MAR) mechanism. Missing postbaseline data for patients randomized but not treated will be imputed by the respective baseline value (baseline observation carried forward, BOCF). Intermediate missing data of Day 14 (ie, NIAID assessments prior Day 14 and at Day 28 are available, but only Day 14 is missing) will be imputed by Last-observationcarried-forward (LOCF). The comparison between the treatment groups will be performed on the ITT after imputation of missing values using MH test for common risk difference considering the 4 strata resulting from the 2 randomization stratification factors disease severity (moderate versus severe) and age-class (≤65 years versus >65 years). 95% confidence interval (CI) will be provided for the risk difference.

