8.1. General Methods

SAS® version 9.4 or higher will be used for all statistical analyses and tabulations.

In general, summaries will present data by treatment group and overall for each scheduled assessment time where appropriate. Efficacy, PK and PD summaries will be presented by treatment group, only.

Unless stated otherwise, descriptive summaries will be presented as follows: Continuous and ordinal variables will be summarized by the number of patients (N), mean, standard deviation, median, minimum, and maximum for actual values and change from baseline. Additionally, for ordinal data, the number and percentage of patients in each category will be presented. Binary and categorical variables will be summarized by treatment group by presenting the number and percentage of patients in the categories.

Statistical tests for comparison between treatments for all defined estimands and endpoints of efficacy will be performed using a two-sided alpha level of 10%. No adjustment for multiple testing will be applied in this descriptive proof-of-concept study. Additionally, 95% confidence intervals will be provided.

Adverse events and medical history will be coded according to the most recent version of Medical Dictionary for Regulatory Activities (MedDRA). Prior and concomitant medications will be coded using the most recent WHO Drug Dictionary version. The actual version of MedDRA and WHO drug used will be noted in the footnote of the respective output. Unless otherwise specified, summaries will be presented for each treatment and overall.

If there are multiple assessments collected for the same scheduled time, the last available assessment before start of study treatment will be used as baseline value and the first assessment at the respective post-baseline visit will be used for post-baseline summarization, except for COVID-19 test results where the last assessment at the post-baseline visit will be used for post-baseline summarization.

All relevant patient data will be included in listings. All patients entered into the database will be included in patient data listings.

Data collected at unscheduled visits will be included in the data listings but will not be included in the analyses or in treatment summaries except unscheduled COVID-19 test results.

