9.5. Medication

Prior medication is defined as any medication which has an end date prior to the date of first dose of study drug administration.

Concomitant medication is defined as any medication which starts before the last dose of study drug and has an end date after the date of first dose of study drug administration or missing.

The original verbatim terms collected in the eCRF for prior and concomitant medications will be coded using the World Health Organization Drug Dictionary (WHO-DD current version).

Listings will include the therapeutic (ie, the second level of Anatomical Therapeutic Chemical [ATC] classification system code that is corresponding to the first 3 figures), preferred name (the fourth level of the ATC code, that is, corresponding to the first 5 figures) and verbatim text. The listings will be sorted by treatment group, patient ID, chronological start date, stop date, therapeutic class, preferred name and verbatim name and will contain all randomized patients.

A frequency table of the number and percentage of patients will be provided for prior medications and concomitant medications by therapeutic class and preferred name for each treatment group and overall on the ITT.

Non-drug therapies collected on the eCRF will be listed and summarized by number and percentage of patients.

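### The dexamethasone/remdesivir subgroup in SAP section 8.6 is defined by use during study treatment, so its arm comparison is open to bias of unknown size and direction

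*SAP*

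**What the plan says.** SAP section 8.6 states: "Descriptive summaries of efficacy for the primary efficacy endpoint and for the key secondary efficacy endpoints will be repeated on the subgroups". The list covers COVID-19 severity, age-class, vaccination status, an obesity class by BMI, and "patients taking Dexamethasone and/or Remdesivir during treatment with study drug". Severity and age-class are randomisation strata, and vaccination and BMI carry no on-treatment wording. The dexamethasone/remdesivir factor is the only one tied to the treatment period, and the only one for which no comparison group is named or evident.

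Other sections determine how this works in practice:

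- Section 8.1: "Efficacy, PK and PD summaries will be presented by treatment group, only". The subgroup table therefore sets MP1032 beside placebo.
- Section 4.1: "All patients will be treated for 28 days, unless the study drug is discontinued". The period in which a patient can become a user runs up to Day 28.
- Section 4.1: "Each site will treat all patients with SoC for the duration of the study". The choice of SoC follows the hospital's own procedures.
- Section 9.5 counts as concomitant "any medication which starts before the last dose of study drug and has an end date after the date of first dose". Drugs already running at first dose and drugs started later are pooled.
- Section 5.1 gives the primary endpoint as "Proportion of patients with disease progression on Day 14".

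Section 10.4 cautions about bias for exploratory endpoints that exist only in part of the randomised population. Section 8.6 has no such caution.

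**The concern.** A subgroup supports a fair comparison of arms when membership is fixed before randomised treatment can act. Here it need not be. A patient can become a user on Day 3 because of worsening, or on Day 20, after the Day 14 outcome is known. If clinical course influences who starts these drugs, users are selected partly on the outcome being summarised. If MP1032 also changes who is started, the selection differs between arms.

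The window also closes with study drug. Read literally, a patient who stops study drug and starts dexamethasone the next day is not in the subgroup, so discontinuation affects membership as well.

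At stake is how the table is read. MP1032 is tested on top of standard care, and a natural question is whether it adds anything in patients receiving these two drugs. A by-arm table in on-treatment users looks as if it answers that question, but part or all of any difference in it could come from selection. Summarising baseline characteristics within the subgroup, which section 8.6 also plans, does not remove this.

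**Working it through.** **Plan's own figure.** The SAP states no figure for this subgroup. The planning rates used below come from section 4.3: 10% progression on MP1032, 30% on placebo, two-sided alpha 10%, 76 + 38 = 114 patients, power 83%. Pooled-variance chi-square without continuity correction:

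- Pooled rate = (38 × 0.30 + 76 × 0.10)/114 = 0.1667.
- Standard error under the null = sqrt(0.1667 × 0.8333 × (1/38 + 1/76)) = 0.0740.
- Standard error under the alternative = sqrt(0.21/38 + 0.09/76) = 0.0819.
- z = (0.20 - 1.645 × 0.0740)/0.0819 = 0.955, so power is 83.0%. With 5% early terminations, 114/0.95 = 120.

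The design figure reproduces, and the rates are used as given.

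**Illustration 1: starting depends on outcome only.** The SAP gives no usage rates, so these are assumptions:

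- b = share already on the drugs at baseline, equal in both arms and unrelated to risk
- s1 = probability that a progressor not on the drugs at baseline starts them
- s0 = the same for a non-progressor

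Then u1 = b + (1 - b)s1 and u0 = b + (1 - b)s0. With p the arm's true progression rate:

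- Users' risk = p·u1 / [p·u1 + (1 - p)·u0]
- Non-users' risk = p(1 - u1) / [p(1 - u1) + (1 - p)(1 - u0)]

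Example with b = 0, s1 = 0.8, s0 = 0.2:

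- MP1032 users: 0.08/(0.08 + 0.18) = 30.8%.
- Placebo users: 0.24/(0.24 + 0.14) = 63.2%.
- Difference: -32.4 points, where the truth is -20 in everyone.

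Apparent difference among users, in points:

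| Baseline use b | s1/s0 = 0.5/0.2 | 0.8/0.2 | 0.9/0.1 |
|---|---|---|---|
| 0 | -30.0 | -32.4 | -29.4 |
| 0.3 | -24.7 | -27.7 | -30.0 |
| 0.6 | -22.0 | -23.6 | -24.8 |
| 0.9 | -20.4 | -20.8 | -21.0 |

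If non-users were tabulated, they would show -14.6, -7.0 and -3.3 points in the three columns, whatever b is below 1. There is no distortion if s1 = s0, and none among users if b = 1.

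**Odds ratio in illustration 1.** Overall it is (0.10/0.90)/(0.30/0.70) = 0.259. Among users, u1/u0 multiplies the odds in both arms and cancels. In the example, (0.08/0.18)/(0.24/0.14) = 0.259. The shift is on the risk-difference scale only.

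**Illustration 2: starting also depends on arm, with no true effect.** Assume progression is 30% in both arms. A high-risk 30% of patients progress in 70%, so the rest progress in (0.30 - 0.30 × 0.70)/0.70 = 12.9%. High-risk patients start the drugs in 80% in both arms. Low-risk patients start in 40% on placebo and in 30%, 20% or 10% on MP1032.

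With b = 0 and 10% on MP1032:

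- MP1032 users: (0.168 + 0.009)/(0.24 + 0.07) = 57.1%.
- Placebo users: (0.168 + 0.036)/(0.24 + 0.28) = 39.2%.
- Difference: +17.9 points, all of it false.

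Across the three MP1032 starting rates, the false excess is +4.1 to +17.9 points at b = 0, +1.8 to +6.3 at b = 0.3, and at most +0.4 at b = 0.9. Exchanging the arms' starting rates reverses the sign.

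**After a baseline definition.** Membership cannot depend on arm or later outcome. If 10% and 30% apply equally to baseline users and non-users, the expected difference is -20 points in both groups.

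**The case against.** The strongest reply is that little bias may arise. Patients are in hospital with moderate to severe disease and receive hospital SoC throughout, and drugs already running at first dose count. If 90% of patients are on the drugs at baseline, illustration 1 gives -20 to -21 against a true -20. This stands as a limit on size. It does not support the definition, because the SAP neither states baseline use nor separates it from later use.

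Second, illustration 1 leaves the odds ratio at 0.259, so it changes base risk without creating a relative effect. That is correct. A false effect needs starting to depend on arm as well, as in illustration 2.

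Third, section 8.6 plans descriptive summaries with no subgroup or interaction test, and attaches no decision to them. That also stands and holds the severity down.

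Some stronger readings go beyond the document:

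- A reader might infer that membership is driven by the outcome and that the comparison is biased. The SAP does not say when or why these drugs are started. It shows only that membership can depend on clinical course.
- A reader might infer that a uniform effect would appear confined to users. That needs every progressor to receive the drugs, and a non-user table that section 8.6 does not commit to. Without the first assumption, the illustrated non-user difference is -3 to -15 points.
- A reader might take section 7.1, "All events leading to study treatment discontinuation and/or switch to other treatment prior to Day 14 will be handled using the treatment-policy strategy", as a second instance. It is not: that estimand analyses all randomised patients and does not condition on these drugs.

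**Conclusion.** The point holds in limited form. As worded, the subgroup can be populated after randomisation, even after the Day 14 endpoint, and no other section repairs this. Its arm comparison is open to bias of unknown size and direction. How large depends on how much use begins after first dose, which the SAP does not give. Under the assumed starting rates, the distortion of a true -20 points among users runs from under 1 point (90% baseline use) to about 12 points (no baseline use). If starting also depends on arm, a difference can appear where there is none.

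The primary ITT analysis and its error rate are unaffected. Severity is modest: the definition should be corrected because the table invites an add-on interpretation it cannot support.

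**What to change.** In section 8.6, define the factor as dexamethasone and/or remdesivir use at or before the first dose of study drug, yes versus no, and show both levels by arm. Report initiation after first dose by arm as a separate post-baseline description, not as a group within which efficacy is compared.

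The cost is about one sentence in the SAP plus a date convention. No new data are needed, because section 9.5 already sorts the medication listings by start and stop date. The convention matters because section 8.3 places a missing or incomplete concomitant-medication start date within study treatment unless the partial date shows otherwise. Under the new definition, that would count undated use as not present at baseline. The SAP should say how such records, and starts on Day 1 with no clock time, are classified, and fix this before unblinding.

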9.1. Patient Disposition and Withdrawals

Patient disposition data will be listed. Summary tables reflecting the number of patients for the following will be presented:

- Screened and randomized patients
- ITT, PPS, SS and PKS
- Patients who completed 14 days of treatment
- Patients who early terminated and did not complete 14-days of study treatment with reasons for early treatment termination
- Patients who completed the 28-days treatment period
- Patients who early terminated the 28-days study treatment period with reasons for early treatment termination
- Patients who early terminated the study treatment but are followed up until Day 28
- Patients who early terminated the study treatment but are followed up until Day 60
- Patients who completed the study including the follow-up period (Day 60), after having completed study treatment
- Patients who early terminated the study after having completed the treatment period with reasons for early study termination

Screen Failure subjects will be listed with reason for failure.

9.2. Demographic and Baseline Characteristics

Demographic characteristics such as sex, age, race, ethnicity, height, weight and BMI at screening will be summarized for ITT and SS, by treatment and overall. Number and percentage of patients with age <65 years and >65 years and number and percentage of patients in the disease severity moderate and severe will be presented by treatment group and overall for the ITT and the SS. Additionally, demographic characteristics will be summarized for each country by treatment group and overall for the ITT. In case of identification of relevant heterogeneity in the distribution between countries, supportive analyses of efficacy for comparison between the treatments will consider country (or at least region) as nominal variable within the respective model. Demographic characteristics will be listed for all randomized patients.

BMI (kg/m²) = Weight (kg)/[Height (m)²]

9.3. Medical and Surgical History

Medical and surgical history will be coded using current version of MedDRA®. Medical and surgical history will be listed for all randomized patients. Medical and surgical history will be summarized by System Organ Class (SOC) and Preferred Term (PT) for each treatment group and overall.

This document is confidential.

SAP Text Version: 2.0, 31-Aug-2022 Controlled Document ID: CC Effective Date 31-Aug-2020 Filing requirements: TMF

Page 33 of 56

9.4. Other Baseline Characteristics

NIAID at baseline will be summarized by number and percentage of patients in each category by treatment group and overall for ITT and SS.

9.5. Medication

Prior medication is defined as any medication which has an end date prior to the date of first dose of study drug administration.

Concomitant medication is defined as any medication which starts before the last dose of study drug and has an end date after the date of first dose of study drug administration or missing.

The original verbatim terms collected in the eCRF for prior and concomitant medications will be coded using the World Health Organization Drug Dictionary (WHO-DD current version).

Listings will include the therapeutic (ie, the second level of Anatomical Therapeutic Chemical [ATC] classification system code that is corresponding to the first 3 figures), preferred name (the fourth level of the ATC code, that is, corresponding to the first 5 figures) and verbatim text. The listings will be sorted by treatment group, patient ID, chronological start date, stop date, therapeutic class, preferred name and verbatim name and will contain all randomized patients.

A frequency table of the number and percentage of patients will be provided for prior medications and concomitant medications by therapeutic class and preferred name for each treatment group and overall on the ITT.

Non-drug therapies collected on the eCRF will be listed and summarized by number and percentage of patients.

9.6. Extent of Exposure

Number and percentage of patients who received study treatment for the first 14 days, and who completed all 28 days of study treatment will be presented by treatment group and overall. The total duration of treatment and the total number of capsules received within the first 14 days and within 28 days will be summarized by treatment group on the SS and ITT, as appropriate. A listing presenting all above defined variables of extent of exposure will be presented for the randomized patients.

9.7. Treatment Compliance

During hospitalization, the administration of the study drug will be performed by the investigator (or qualified blinded designee) to ensure compliance. If the patient is discharged home before Day 28, the study team will provide the patient with the remainder of the assigned blinded study treatment kit(s) to take home along with instructions to continue treatment at home; for these patients, treatment compliance will be assessed via a diary. If the patient does not feel comfortable to complete the diary, the site will alternatively provide the patient with the option to be called twice a day, to confirm that the study drug is taken as instructed. Patients are to be reminded of the importance of compliance with their assigned regimen, with an emphasis on taking their study drug on schedule and maintaining the prescribed interval between doses.

Investigators will maintain records that adequately document that the patients were provided with the correct study treatment kit(s) and reconcile the products received from the drug dispensing center.

Treatment compliance in % will be calculated as

(Total number of capsules taken / 12) / treatment duration (days) x 100%

This document is confidential.

SAP Text Version: 2.0, 31-Aug-2022 Controlled Document ID: CC , Effective Date 31-Aug-2020 Filing requirements: TMF

Page 34 of 56

The treatment compliance will be calculated for the first 14 days of treatment and for the whole 28 days treatment and will be summarized by treatment group and overall on the SS and ITT, as appropriate.

Noncompliance is defined as taking <80% or >120% of study drug. The number and percentage of patients with non-compliance will be presented by treatment group and overall on the SS and ITT, as appropriate.

A listing including all above defined variables of treatment compliance will be presented for the randomized patients.

This document is confidential.

Page 35 of 56
10. Efficacy

All efficacy endpoints will be summarized using descriptive statistics by treatment group and by visit, as appropriate: Binary and categorical endpoints will be summarized by treatment group by presenting the number and percentage of patients in each category. Continuous and ordinal endpoints will be described by mean, standard deviation, median, minimum, and maximum for actual values and change from baseline. Additionally, for ordinal data, the number and percentage of patients in each category will be presented. Statistical tests for the comparison between treatments will be performed using a two-sided alpha of 10%.

